# **5. STUDY PROCEDURES**

# Study visits, procedures, data collection, and testing

Participants will be recruited and enrolled in an ongoing manner until the study goal of 250 participants for Aim 1 is reached. We expect 100 (40%) to have high PAP >40mmHg estimated by echocardiography based on preliminary data. This group (in addition to individuals referred for clinically-indicated RHC or CPET) will undergo invasive CPET testing with hemodynamic monitoring and PAEC phenotyping as part of Aim 2. Of this sample, we expect 75 participants will have abnormal pulmonary hemodynamics as measured by RHC, given significant correlation between invasive and non-invasive measures of PAP (r=0.77). These individuals will part-take in Aim 3 of the study. A flowsheet of the study schedule is provided in **Figure 1**, and data collected is outlined in **Table 2**.

Because fasting blood work will be obtained at the time of Study Visits 1, 3, and 4, the participant will be instructed to fast with no eating or drinking after midnight prior to those visits.

Visit 1 (Screening): At the first study visit, participants will undergo informed consent as outlined above. Information on age, gender, and race/ethnicity will be obtained. A medical history will be obtained by study staff, which includes information on current and past medical issues, medications, and allergies to past medications in order to identify possible study contraindications. Dyspnea will be assessed using the modified Medical Research Council scale (mMRC). Seated blood pressure and pulse will be checked. Anthropometric measures will be taken: weight and height will be measured in order to calculate BMI, and waist circumference will be measured. Fasting blood work will be obtained, including glucose, insulin, lipid profile, hemoglobin A1c, and C-reactive protein. We will collect up to 100 ml of blood for these measurements and storage of samples for future use. Participants will also undergo an electrocardiogram (ECG), optional standard 2-hour oral glucose tolerance test (OGTT), optional 6-minute walk test (6MW), transthoracic echocardiography, and collection of venous endothelial cells as detailed below:

**ECG:** A standard 12-lead electrocardiogram will be performed.

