**2-hour OGTT (optional)**: A blood glucose (BG) measurement will be checked in order to assure safety in proceeding with an OGTT, and a pre-OGTT value of > 200mg/dL is listed as a clear stopping rule for the protocol. If there is no contraindication, the participant will receive a 75g oral glucose load and begin an OGTT. An IV will be inserted and levels of insulin and glucose will be measured at 0, 30, and 120 minutes following the OGTT. For the OGTT samples, 40cc of blood is needed.

**Venous endothelial cell collection:** The venous endothelial cell collection occurs during Study Visit 1, during which participants already undergo IV placement as part of the oral glucose tolerance test, as well as during Study Visit 4. After IV insertion using sterile technique, a standard guide wire (J-wire) is inserted into the vein through the IV and then removed and processed, with collection of up to 4 wires. A vast array of wires of introducer wires are approved by the FDA and are used clinically for the insertion of central and peripheral catheters into veins and are designed to be atraumatic. With respect to safety, insertion of the J wire once the IV has been placed is painless. It is associated with possible bleeding or bruising associated with placement of the IV, and a potential risk of thrombophlebitis. The technique has been applied safely over 2,000 times in [name] laboratory without reported adverse effects, and MGH co-investigators have undergone formal training in her laboratory. 83,84 Only sterile IV sites will be used for this procedure. The de-identified coded specimen is transferred to the

laboratory of [name] (co-investigator), where the wire is carefully washed and cells are collected for analysis. No immortalized cell lines will be established from the harvested cells.

**6MWT (optional)**: We will perform standardized 6MW testing according to published guidelines. We will record oxygen saturation, blood pressure, and heart rate at the start of the test, and assess dyspnea (as measured with the modified Borg dyspnea scale) at the start and end of the 6MW test. Established reference ranges will be used to evaluate 6MW distance relative to age and sex.

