Visit 2 (Study procedures): At the second visit, any updates on medical history will be ascertained. Seated blood pressure and heart rate will be checked. Blood work will be obtained, and we will collect up to 150 ml of blood for these measurements and storage of samples for future use. Study volunteers who have not previously undergone clinically-indicated CPET testing will then undergo right heart catheterization (RHC), cardiopulmonary exercise testing (CPET), radionuclide ventriculography, with collection of pulmonary artery endothelial cells (PAEC) for research purposes as detailed below. For interested participants who have previously completed clinical CPET testing, Visit 1 and 2 will be combined, and clinical CPET testing results will be reviewed without the need to repeat the Visit 2 CPET. For interested participants who previously underwent right heart catheterization (RHC), Visit 1 and 2 may be combined without the Visit 2 CPET. The following criteria must be met to justify RHC and CPET for research purposes:

- A. Participants must be symptomatic with evidence of ≥ grade 1 dyspnea based on the modified Medical Research Council scale
- B. Participants with the most common treatable causes of chronic dyspnea are excluded from our study, as explicitly outlined in our exclusion criteria (existing diagnosis of pulmonary arterial hypertension, severe COPD or asthma, obstructive sleep apnea, chronic kidney disease or liver disease, anemia).
- C. Participants with otherwise unexplained dyspnea then undergo comprehensive transthoracic echocardiography in order to assess estimated pulmonary artery systolic pressures. Based on this noninvasive testing, participants who have pulmonary artery systolic pressure ≥ 40mmHg and who otherwise have no contraindications to RHC and CPET then qualify for this testing in our protocol. This approach is in line with the standard of care and is supported by the American College of Cardiology/ American Heart Association 2009 Expert Consensus Document on Pulmonary Hypertension, which states that based on echocardiography, an estimated "pressure of greater than

40mmHg generally warrants further evaluation in the patient with unexplained dyspnea" (McLaughlin VV et al, *Circulation*, 2009).

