Metformin or placebo administration: The participant will then receive, at random, either metformin or placebo in a 1:1 blinded fashion. Randomization will be stratified by type of PH (resting vs exercise-induced) and will be performed in blocks of 4 to assure balanced group sizes. Because we wish to ensure equal gender representation into the treatment and placebo groups, randomization will be done separately for men and women. Participants will be given 500mg capsules of metformin or matching placebo and instructed to take 500mg twice daily for 1 week, followed by 1g twice daily for a total of 3 months. Participants may receive study medication by mail or at study visits. We will exclude individuals with contraindications to metformin use as outlined in the exclusion criteria, and participants will be monitored for clinical symptoms of lactic acidosis and hypoglycemia. Medication compliance will be assessed with pill counts. The proposed use of metformin is IND-exempt.

Visit 3 (Interim): The third study visit will take place at MGH or remotely, approximately 2-4 weeks after initiation of metformin or placebo. An interim medical history will be taken by study staff in person or by telephone to assure that no contraindications to study participation or potential side effects have developed. Seated blood pressure and pulse may be obtained, and weight may be measured. Fasting blood work will be obtained at MGH or a local lab. We may collect up to 100 ml of blood for these measurements and storage of samples for future use.

Visit 4 (Interim): The fourth study visit will take place approximately 7-12 weeks after initiation of metformin or placebo. An interim medical history will be taken to assure that no contraindications to study participation or potential side effects have developed. Seated blood pressure, pulse, and anthropometrics will be obtained. Fasting blood work will be obtained. We will collect up to 100 ml of blood for these measurements and storage of samples for future use. Participants will undergo venous endothelial cell collection as outlined previously, as well as an electrocardiogram (ECG).

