Visit 5 (Final measures): At the fifth study visit approximately 3 months ( $\pm$  2 weeks) after initiation of metformin or placebo, final measures will be obtained. Seated blood pressure and pulse will be obtained. Blood work will be obtained. We will collect up to 150 ml of blood for these measurements and storage of samples for future use. Participants will then undergo invasive CPET with hemodynamic monitoring and PAEC cell collection as outlined previously. In order to minimize participant burden, repeat invasive CPET testing may be conducted without invasive arterial monitoring or first-pass radionuclide ventriculography.

Study staff members are available for questions at any time throughout the study, and contact numbers are provided to the subject. At the end of each study visit, participants will be given the opportunity to ask any questions regarding the study.

Research subjects who complete the study will be compensated for their time and efforts, according to each visit completed as follows: Visit 1 \$50, Visit 2 \$150, Visit 3 \$50, Visit 4 \$50, Visit 5 \$250. If the subject withdraws from the study, they will receive payment for the visits that were completed. Subjects will be paid upon completion of each visit. We will also provide parking vouchers for study visits.

Additional Visits: If a visit involving invasive CPET (Visit 2 or Visit 5) is scheduled more than 30 days after Visit 1 or Visit 4, respectively, then research subjects may be asked to attend an additional visit

prior to CPET in order to obtain pre-requisite labs and electrocardiogram guided by cath lab safety protocols. Subjects will be compensated \$50 and a parking voucher for each such additional visit.

Research subjects may be asked to complete a COVID test (e.g. nasopharyngeal swab) prior to procedures, such as the CPET. This follows institutional guidelines to ensure the safety of hospital staff and patients. Required pre-procedure COVID testing will be paid for by the study fund. Subjects will be compensated \$20 per COVID test.

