#### 7. RISKS AND DISCOMFORTS

#### **Procedures**

Phlebotomy and IV placement: In order to minimize the risks of phlebotomy, participants will be asked about previous difficulty with phlebotomy (particularly pre-syncope or syncope) and appropriate measures will be taken, as needed. During venipuncture, the participant will be in a sitting position. At each study visit, no more than 150 cc of blood is taken, and in total over the course of the study, no more than 450 cc (2 cups) of blood will be obtained. This is within the Red Cross guidelines (less than 500 cc every 2 months). Risks of phlebotomy include anemia, and the amount of blood collected will be reduced if the investigator feels there is a significant risk of anemia. Other risks include discomfort, bleeding or bruising where the needle enters the skin, and rarely, fainting or infection may occur.

Protection against risk: The participants will be asked whether they are feeling well during the blood draw and throughout the visit. If the participant is not feeling well, the specific discomfort will be addressed, and the participant will be referred for evaluation, as needed. If a participant feels lightheaded during the venipuncture or blood draw, the procedure is suspended. The participant will be provided with orange juice and observed until the light-headedness resolves. If the participant is willing, s/he may continue the protocol once this symptom has resolved. If anemia is identified at any time during the study (Hemoglobin, Hb  $\leq$  9 g/dL), no further blood draws will be conducted until Hb is again documented as Hb  $\geq$  9 g/dL.

**6-minute walk test:** The 6-minute walk test is a simple and practical non-invasive test to evaluate functional capacity. Rarely there may be an increased risk of arrhythmias or cardiovascular collapse. However, each participant determines the level and intensity of walking during the test, and it has been performed on thousands of older persons and patients with heart failure or cardiomyopathy without serious adverse events. Rarely Participants with absolute contraindications are already excluded from the study as outlined in Table 1 (unstable angina, myocardial infarction in previous month). Relative contraindications include a resting heart rate > 120 bpm, or uncontrolled hypertension (systolic blood pressure > 180 mmHg, diastolic blood pressure > 100 mmHg).

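### The visit-by-visit blood ceilings add up to 600 ml for a participant who completes Aim 3, against a stated whole-study maximum of 450 cc

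*Protocol*

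**What the plan says.** Protocol Section 7, under Procedures (phlebotomy and IV placement), limits each visit to 150 cc and then states that "in total over the course of the study, no more than 450 cc (2 cups) of blood will be obtained". It describes this as consistent with a Red Cross limit of less than 500 cc every two months. The same paragraph names anemia as a risk and says that "the amount of blood collected will be reduced if the investigator feels there is a significant risk of anemia". Draws stop while hemoglobin is at or below 9 g/dL.

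Protocol Section 5 (study visits and procedures) gives the volumes by visit:

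- Visit 1: "We will collect up to 100 ml of blood for these measurements and storage of samples for future use". For the optional glucose tolerance test at this visit: "For the OGTT samples, 40cc of blood is needed".
- Visit 2: "we will collect up to 150 ml of blood for these measurements and storage of samples for future use".
- Visit 3: "We may collect up to 100 ml of blood for these measurements and storage of samples for future use".
- Visit 4: the same sentence and the same 100 ml as Visit 1.
- Visit 5: "We will collect up to 150 ml of blood for these measurements and storage of samples for future use".

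Section 5 also allows an additional visit when an invasive exercise test falls more than 30 days after Visit 1 or Visit 4. Its purpose is "prior to CPET in order to obtain pre-requisite labs and electrocardiogram guided by cath lab safety protocols", and no volume is given. Visits 1 and 2 may be combined for participants with earlier clinical testing, again with no volume stated for the combined visit.

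**The concern.** The 450 cc figure is a participant protection in the risk section. Ethics reviewers and others who read that section will take it as the most blood anyone gives. The schedule that staff work from allows more. A coordinator could draw the permitted amount at every visit, respect the 150 cc visit limit each time, and pass 450 cc at Visit 5 without any visit-level instruction having been broken. Drawing to the ceiling is also a realistic course, because each ceiling explicitly covers blood stored for future use as well as the scheduled tests.

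What is at stake is the accuracy of a stated safety limit for the Aim 3 participants, a target of 75 out of 250. No trial result depends on it.

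**Working it through.** **Inputs.** Visit ceilings from protocol Section 5: V1 = 100, V2 = 150, V3 = 100, V4 = 100, V5 = 150 ml. Glucose tolerance test (OGTT) = 40 ml, optional. From Section 7: 150 ml per visit, 450 ml per study, less than 500 ml per two months.

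**1. Trying to reproduce 450.** The five ceilings do not give it. Only two subsets do, both without the OGTT:

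- V1 + V2 + V3 + V4 = 100 + 150 + 100 + 100 = 450, which leaves out the final visit.
- V1 + V3 + V4 + V5 = 100 + 100 + 100 + 150 = 450, which leaves out the Visit 2 draw.

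Neither describes a participant drawn to the ceiling at all five visits.

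**2. Full Aim 3 schedule.**

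- Without OGTT blood: 100 + 150 + 100 + 100 + 150 = 600. Excess 600 − 450 = 150; 600/450 = 1.33.
- With OGTT blood additional: 600 + 40 = 640. Excess 190; 640/450 = 1.42.
- No single visit exceeds 150 ml. Visit 1 with the OGTT is 100 + 40 = 140.

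**3. More lenient readings.**

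| Scenario | Sum (ml) | Against 450 |
|---|---|---|
| No Visit 3 draw, no OGTT | 100 + 150 + 100 + 150 = 500 | 50 over (11%) |
| Visits 1 and 2 combined, held to 150 | 150 + 100 + 100 + 150 = 500 | 50 over (11%) |
| Combined visit and no Visit 3 draw | 150 + 100 + 150 = 400 | under |
| Aims 1 and 2 only | 100 + 150 = 250 (290 with OGTT) | under |

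The rows without a Visit 3 draw are generous to the plan. Table 2 lists a metabolic panel and lactic acid at Visit 3, and the drug side effects part of Section 7 requires blood at the 2-to-4-week visit for kidney function, glucose and lactic acid.

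**4. The two-month statement.** Assume drug starts at Visit 2 (day 0), with Visit 3 at day 14–28, Visit 4 at day 49–84 and Visit 5 at day 77–105.

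- The largest sum in any 60- to 62-day window is Visits 1 to 4 with the OGTT: 140 + 150 + 100 + 100 = 490, below 500. It needs Visit 1 shortly before Visit 2 and Visit 4 at the start of its window.
- An additional visit before Visit 2 arises only if Visit 2 is more than 30 days after Visit 1. Visits 1 and 4 are then at least 31 + 49 = 80 days apart. The window holds 140 + 150 + 100 = 390 plus the extra draw, so the limit is kept if that draw is below 110 ml.
- Before Visit 5, the corresponding sum is 100 + 100 + 150 = 350 plus the extra draw.

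**The case against.** The strongest reply is that nothing contradicts anything. The visit figures are upper limits, Visit 3 is worded as optional, and a whole-study cap may sit below the sum of the visit caps. On that reading Section 7 governs, and anyone who draws more than 450 cc has broken it. This is logically sound, and it is why the point is about what the schedule permits and not about a certain breach. It does not remove the gap. To stay within 450 ml, draws would have to average 450/600 = 75% of the ceilings, and no text asks for that, requires a cumulative record, or says which draw to shorten. The only reductions are for anemia.

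The 640 ml figure can also be challenged, since the fasting OGTT sample might double as the Visit 1 fasting sample. That is fair, and the figure is conditional for this reason. The 600 ml figure does not depend on it.

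It is tempting to explain the mismatch by the IRB notice for the protocol dated 2 July 2018, which records larger draws at exercise-test visits and an added interim visit. A total that was never updated would fit, but so would a deliberate cap, and the documents do not settle it.

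Finally, the practical effect is small: the anemia safeguards stand and the two-month limit is not shown to be exceeded. That bears on how serious the point is, not on whether it is correct.

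**Conclusion.** The point holds. The current schedule allows 600 ml for a participant who attends all five visits, 150 ml (33%) more than the 450 cc stated in Section 7. The figure is 640 ml (42% more) if the optional OGTT blood is additional to the Visit 1 ceiling. Leaving out the Visit 3 draw, or combining Visits 1 and 2 at 150 ml, still allows 500 ml without extra OGTT blood. Only both together bring the sum under the cap.

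The conclusion assumes draws at the ceilings. It applies to Aim 3 participants only. The two-month statement survives on the stated volumes, given drug start at Visit 2 and an additional-visit draw below 110 ml. This is a participant-protection figure worth correcting; it has no bearing on endpoint, analysis or power.

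**What to change.** The investigators should decide which figure is intended and choose one of two routes.

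- **Keep 450 ml.** Either lower the visit ceilings so that they sum to 450 or less (about 450/600 = 75% of present values, or 450/640 = 70% if the OGTT blood is additional), or leave the ceilings and require a running total for each participant, with draws trimmed once 450 ml is reached.
- **Restate the total.** Give 600 ml (640 ml if the OGTT blood is additional) in Section 7. Keep the two-month statement only after setting a volume for additional visits.

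Under either route, state whether the 40 cc for the OGTT lies inside the 100 ml at Visit 1, and that a combined Visit 1 and 2 is held to 150 cc.

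The cost is a wording amendment. The first route leaves somewhat less stored blood; the second shows a less favourable total.

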# Drug side effects and toxicities

Metformin administration: This drug has been on the market for several decades and is considered first line therapy for diabetes mellitus type 2. Moreover, it has been used extensively in non-hyperglycemic patients with polycystic ovarian disease. Additional studies of the safety of metformin in heart failure have been published. The pertinent risk of metformin is development of lactic acidosis. This risk has been reported primarily in patients with abnormal renal or hepatic function, thus we have chosen to exclude these populations from the study. Additional concerns include hypoglycemia, though this is a rare risk for this drug, particularly in the absence of other hypoglycemic medications (an exclusion criterion for our study), and gastrointestinal distress. Patients will be educated on the signs and symptoms of hypoglycemia and advised to contact study staff immediately if any arise. We will monitor patients by telephone 1 week after metformin initiation, and an interim visit will be conducted 2-4 weeks after metformin initiation, at which point labs will be drawn to evaluate kidney function, glucose, and lactic acid levels. If patients report significant gastrointestinal effects, metformin will not be increased as would otherwise occur in the protocol. If symptoms persist further, the dose will be dropped by 500 mg daily to the highest tolerated dose.

The most common adverse reactions experienced are:

- >10% of patients: diarrhea (instant release tablet: 12% to 53%; extended release tablet: 10% to 17%), nausea/vomiting (instant release tablet: 7% to 26%; extended release tablet: 7% to 9%), flatulence (12%), Weakness (9%).
- 1% to 10%: chest discomfort, flushing, palpitation, headache (6%), chills, dizziness, lightheadedness, rash, hypoglycemia, Indigestion (7%), abdominal discomfort (6%), abdominal distention, abnormal stools, constipation, dyspepsia/ heartburn, taste disorder, myalgia, dyspnea, upper respiratory tract infection, decreased vitamin B12 levels (7%), increased diaphoresis, flulike syndrome, nail disorder.
- <1% (Limited to important or life-threatening): lactic acidosis, leukocytoclastic vasculitis, megaloblastic anemia, pneumonitis. Lactic acidosis is a rare but serious side effect due to metformin accumulation. When lactic acidosis occurs it is fatal in approximately 50% of cases. Symptoms include malaise, myalgias, respiratory distress, increasing somnolence, and nonspecific abdominal distress.

Contraindications to the use of metformin are: hypersensitivity to metformin or any component of the formulation; renal disease or renal dysfunction (serum creatinine ≥1.5 mg/dL in males or ≥1.4 mg/dL in females) or abnormal creatinine clearance from any cause, including shock, acute myocardial infarction, or septicemia; acute or chronic metabolic acidosis with or without coma (including diabetic ketoacidosis). A boxed warning has been issued for metformin related to the risk of developing lactic acidosis. The risk is increased in patients with acute congestive heart failure, dehydration, excessive alcohol intake, hepatic or renal impairment, or sepsis. All of these conditions are exclusion criteria for our study.

Protection against risk: Conditions that increase the risk of lactic acidosis on metformin treatment are all exclusion criteria for this study. We will monitor patients by telephone 1 week after metformin initiation, and an interim visit will be conducted 2-4 weeks after metformin initiation, at which point labs will be drawn to evaluate kidney function, glucose, and lactic acid levels. In addition, metformin therapy will be discontinued prior to or at the time of intravascular administration of iodinated contrast media (potential for acute alteration in renal function) should a subject require contrast during the course of this study. Metformin will be withheld for 48 hours after the radiologic study and restarted only after renal function has been confirmed as normal. Patients will be encouraged to delay any elective

radiologic studies requiring iodinated contrast until the conclusion of the study. Criteria for patient removal will be: symptomatic hypoglycemia or lactic acidosis. The PI will monitor potential side effects, and the study can be discontinued at any time at the subject's request. If the independent safety officer determines that symptomatic lactic acidosis occurs and is attributable to study drug in one patient the study will be stopped altogether. Patients with symptomatic hypoglycemia unresponsive to dose reduction may withdraw. Inability to tolerate metformin or hypersensitivity to drug will trigger withdrawal. Development of renal dysfunction that would preclude enrollment will require withdrawal. Patients who require additional anti-diabetic drugs prior to study completion will continue to be enrolled. Furthermore, the independent safety officer has the ability to stop the study for safety concerns. Any patient who voluntarily withdraws or withdraws because of an aforementioned adverse event will be requested to allow us to continue to accrue clinical data for analysis, if possible. Participants will be monitored for any of the above side effects as outlined above, and will be encouraged to contact the study staff with any interim symptoms. A board certified medical internist (the PI) is available by pager and telephone at all times, if he/she is not physically present, during the study.

